6.12.7. Columbia-Suicide Severity Rating Scale (C-SSRS)

The C-SSRS is an assessment tool that evaluates suicidal ideation and behavior. Information on the C-SSRS scale can be found through the following link: <http://www.cssrs.columbia.edu> (Columbia University Medical Center (WWW)).

Specifically, the following outcomes are C-SSRS categories and have binary responses (yes/no). The categories have been re-ordered from the actual scale to facilitate the definitions of the composite and comparative endpoints, and to enable clarity in the presentation of the results.

Category 1 – Wish to be Dead

Category 2 – Nonspecific Active Suicidal Thoughts

Category 3 – Active Suicidal Ideation with Any Methods (Not Plan) without Intent to Act

Category 4 – Active Suicidal Ideation with Some Intent to Act, without Specific Plan

Category 5 – Active Suicidal Ideation with Specific Plan and Intent

Category 6 – Preparatory Acts or Behavior

Category 7 – Aborted Attempt

Category 8 – Interrupted Attempt

Category 9 – Actual Attempt (nonfatal)

Category 10 – Completed Suicide

Self-injurious behavior without suicidal intent is also a C-SSRS outcome (although not suicide-related) and has a binary response (yes/no).

Composite endpoints based on the above categories are defined below.

- **Suicidal ideation:** A “yes” answer at any time during treatment to any one of the 5 suicidal ideation questions (Categories 1-5) on the C-SSRS
- **Suicidal behavior:** A “yes” answer at any time during treatment to any one of the 5 suicidal behavior questions (Categories 6-10) on the C-SSRS
- **Suicidal ideation or behavior:** A “yes” answer at any time during treatment to any one of the 10 suicidal ideation and behavior questions (Categories 1-10) on the C-SSRS

Given that few or no suicidal ideation or behaviors are anticipated, C-SSRS will be listed by patient and visit. Only patients who show suicidal ideation/behavior or self-injurious behavior without suicidal intent will be displayed (that is, if a patient’s answers are all ‘no’ for the C-SSRS, then that patient will not be displayed). However, if a patient reported any suicidal ideation/behavior or self-injurious behavior without suicidal intent at any time point then all their ideation and behavior will be displayed, even if not positive. Note, missing data should not be imputed.

The Self-Harm Supplement Form is a 1-question form that is completed, at any visit, including baseline visit, that asks for the number of suicidal behavior, possible suicide behaviors, or nonsuicidal self-injurious behaviors the patient has experienced since the last assessment. For

each unique event identified, a questionnaire (Self-Harm Follow-up Form) which collects supplemental information on the self-injurious behavior is to be completed. The Self-Harm data will be listed by patient and visit if number of events on Self-Harm Supplement Form is not zero in the CRF ‘*Self Harm Questionnaire Supplement.*’

6.12.8. Immunogenicity

6.12.8.1. Definitions and Terms

[figure not shown]
The following sample- and patient-related definitions and parameters will be used to describe the immunogenicity data.

6.12.8.1.1. Sample Category Definitions

Samples are classified into the following categories:

- **Unevaluable sample:** Sample could not be tested for antidrug antibody (ADA) due to sample loss, mishandling, or errors in collection, processing, storage, and so on.
- **Antidrug antibody (ADA) Positive sample:** The presences of ADA is detected and confirmed. The samples are reported as positive. If the sample is positive, a titer value is reported.
- **Neutralizing antidrug antibody (NAb) Positive sample:** NAb are reported as detected.
- **Antidrug antibody (ADA) Negative sample:** The presence of ADA is not detected and the assay drug tolerance level is not exceeded.
- **NAb Negative sample:** The presence of NAb is not detected and the assay drug tolerance level is not exceeded.
- **Inconclusive sample:** when ADA/NAb is not detected in a sample but drug is present in the same sample at a level that can cause interference in the ADA/NAb detection method, then the negative ADA/NAb result cannot be confirmed and the sample should be considered inconclusive.
 - Confirmation of a negative ADA or NAb result was based on ixekizumab concentrations.

Figure RHBW.6.4 illustrates the relationship of some of the above terms.

Abbreviation: ADA = antidrug antibody.

[figure not shown]
Figure RHBW.6.4. Sample definitions.

6.12.8.1.2. Patient Category Definitions

The following categories are applied to patients based on the classification of their samples:

- **Unevaluable patient:** a) a patient with no evaluable baseline sample and/or no evaluable postbaseline samples; b) a patient with an evaluable baseline sample but no evaluable postbaseline sample; c) a patient with no evaluable baseline sample, but whose evaluable postbaseline values are all ADA positive or a mix of positive and negative. (Note: If all postbaseline samples are negative, the patient is considered 'evaluable' and will be classified as ADA-negative.)
- **Evaluable patient:** a) Patient with an evaluable baseline sample and at least 1 evaluable postbaseline sample (that is, sample after administration of study drug); b) patient with no evaluable baseline sample whose evaluable postbaseline samples are all ADA negative

Figure RHBW.6.5 illustrates the relationship of the above terms.

Abbreviation: ADA = anti-drug antibody.

Figure RHBW.6.5. Patient categories (evaluable/unevaluable) based on sample status at baseline and postbaseline.

6.12.8.1.3. Definitions for Clinical Interpretation of Assay Results

- Baseline:** For immunogenicity analyses during Period 2, baseline is the last nonmissing observation on, or before, the date of the first injection of study treatment (Week 0). Unless otherwise specified, the baseline for subsequent treatment periods is defined as the last nonmissing observation on, or before, the date of first injection of ixekizumab. For patients originally randomized to ixekizumab during Period 2, baseline is the last nonmissing observation on, or before, the date of the first injection of study treatment for Period 2 (Week 0). For patients who are not originally randomized to ixekizumab in Period 2, baseline is the last nonmissing observation on, or before, the date of the first injection of ixekizumab. See [Table RHBW.6.10](#) for further details.

[figure not shown]
Table RHBW.6.10. Baseline Definition for Immunogenicity Analyses for Extended Treatment Period

Treatment Assignment for Blinded Treatment Dosing Period (Period 2)	Treatment Assignment for Extended Treatment Period (Period 3)	Baseline for Extended Period Analysis ^a
Ixekizumab	Ixekizumab	Week 0
Placebo	Ixekizumab	Week 16

^a Last nonmissing observation on, or before, the date of the first injection of study treatment at the defined week.

- **Baseline ADA positive (pre-existing antibody):** ADA detected in a sample collected at baseline
- **Treatment-emergent antidrug antibody (TE-ADA) positive:** a) a patient with a ≥ 4 -fold increase over a positive baseline antibody titer (Tier 3); or b) for a negative baseline titer, a patient with an increase from the baseline to a level of $\geq 1:10$
- **Baseline ADA-negative:** ADA is not detected in a sample collected at baseline.
- **TE-ADA inconclusive patient:** A patient without a TE-ADA positive sample and with at least 1 sample for which drug levels may interfere with the ADA assay
- **TE-ADA negative patient:** A patient who is evaluable for TE-ADA and is not either TE-ADA positive or TE-ADA inconclusive

Figure RHBW.6.6 illustrates the relationship of some of these terms.

Abbreviation: ADA = anti-drug antibody.

[figure not shown]
Figure RHBW.6.6. Relationship of terms for clinical interpretation of assay results for evaluable patients.

- **Incidence of TE-ADA:** Patients with TE-ADA as a proportion of the evaluable patient population during the treatment period. This excludes unevaluable patients.
- **Follow-up emergent ADA:** ADA is first detected during the follow-up period, after study drug administration is discontinued. This category includes patients negative at baseline who increased to $\geq 1:10$ titer after baseline in the follow-up period or patients ADA positive at baseline and increased at least 4-fold (2 dilutions) over baseline for the first time in the follow-up period.

All ADA positive samples will be evaluated for NAb. Definitions for NAb patient status will be defined as follows:

- **NAb-positive patient:** A patient where a NAb positive result is detected for ≥ 1 TE-ADA positive samples
- **NAb-inconclusive patient:** A patient without a NAb positive sample and with at least 1 sample for which drug levels may interfere with the NAb assay
- **NAb-negative patient:** A patient who is evaluable for NAb and is not either NAb positive sample or NAb inconclusive

A flow chart that reflects the connection between the analytical test results and the clinical interpretation based on the definitions is shown in [Figure RHBW.6.7](#).

Abbreviation: ADA = antidrug antibody; NAb = Neutralizing antidrug antibody; PK = pharmacokinetics.

Figure RHBW.6.7. Flow chart of ADA assessment with clinical interpretation of the various result possibilities.

6.12.8.2. Immunogenicity Analyses

Immunogenicity evaluable patients will be identified as TE-ADA positive, TE-ADA negative, or TE-ADA inconclusive, according to the definitions provided in Section 6.12.8.1.2 and further grouped into TE-ADA status groups and time-varying TE-ADA status groups:

TE-ADA Status Groups:

- TE-ADA status (positive, negative, or inconclusive)
- NAb status (positive, negative, or inconclusive) for TE-ADA positive patients; and
- TE-ADA titer groups for TE-ADA positive patients:
 - Low Titer: TE-ADA titer value (LOCF) <1:160
 - Moderate Titer: TE-ADA titer value (LOCF) \geq 1:160 and <1:1,280
 - High Titer: TE-ADA titer value (LOCF) \geq 1:1,280

Time-Varying TE-ADA Status Groups:

Individual ADA samples will be ascribed into 3 different dichotomous variables as explained in [Table RHBW.6.11](#). Each variable has possible values of a “greater-TE-ADA status” or a “lesser-TE-ADA status,” in the sense that the level of TE-ADA detected in the greater-TE-ADA category is higher than in the lesser-TE-ADA category.

Table RHBW.6.11. TE-ADA Status Dichotomous Variables for AE Analysis

TE-ADA Status Dichotomous Variable	Greater-TE-ADA Status	Lesser-TE-ADA Status
TE-ADA positive	TE-ADA positive	not TE-ADA positive
TE-ADA moderate-to-high	TE-ADA positive with moderate titer or high titer	not TE-ADA positive, or TE-ADA positive with low titer
TE-ADA high status	TE-ADA positive with high titer	not TE-ADA positive, or TE-ADA positive with low or moderate titer

Abbreviations: AE = adverse event; TE-ADA = treatment-emergent antidrug antibody.

Note: For purpose of this analysis, TE-ADA Inconclusive is taken to be “not TE-ADA positive.”

Note: A TE-ADA low is defined as a TE-ADA positive with a titer value <1:160; a TE-ADA moderate is defined as a TE-ADA positive with a titer value \geq 1:160 and <1:1,280; and a TE-ADA high is defined as a TE-ADA positive with a titer value \geq 1:1,280.

For each TE-ADA status dichotomous variable, a time-varying TE-ADA status will be computed. At time t the TE-ADA status is taken to be the highest of the TE-ADA values bracketing time t . More formally, the TE-ADA status at time t is given by the greater of (a) the TE-ADA status at the most-recent postbaseline measurement before t , and (b) the TE-ADA status at the first TE-ADA postbaseline measurement at or after time t . In this computation, “greater” is given by the greater-TE-ADA status of [Table RHBW.6.11](#). If there is no value satisfying criterion (a), then the value (b) is used. Similarly, if there is no value (b), then the value (a) is used.

For each TE-ADA status dichotomous variable, patients will be categorized according to whether they were (i) always in lesser-TE-ADA status postbaseline or (ii) at some point postbaseline, were in greater-TE-ADA status.

6.12.8.2.1. Analyses of Characteristics of ADA Immune Response

The analyses of ADA effects will be conducted on all evaluable patients within the defined safety population for the Blinded Treatment Dosing Period (Period 2), and Combined Blinded Treatment Dosing and Extended Treatment Periods (Combined Periods 2 and 3).

Baseline definition for immunogenicity analyses for the Combined Treatment Period is the same as [Table RHBW.6.10](#).

The overall frequency and percentage (incidence) of patients will be summarized for the TE-ADA status groups and the time-varying TE-ADA status groups. Scheduled visits, unscheduled visits, and repeat measurements will be included.

In addition, the overall frequency and percentage (incidence) of patients will be summarized for the patients who are baseline ADA positive by TE-ADA status groups. For those patients who are TE-ADA positive, a summary of titer values and the proportion of patients who are NAb positive will also be provided.

The time to the development of TE-ADAs (TE-ADA positive, low titer, moderate titer, high titer, and NAb positive) will be calculated as follows:

Time to development of TE-ADAs/NAb (in weeks) = (Date of development of TE-ADAs/NAb – Date of first injection of study treatment + 1) / 7

If a patient has not developed TE-ADAs/NAbs, they will be censored at the date of the last immunogenicity assessment.

Descriptive statistics, including 25th percentile, 50th percentile (median), 75th percentile, and corresponding 95% CIs as well as proportion of TE-ADA/NAb positive by endpoint summarized by treatment group, will also be provided if sufficient data is present. A Kaplan-Meier plot of the time to development of treatment-emergent ADA/NAb will be presented by treatment group, also if sufficient data is present.

For each TE-ADA status dichotomous variable (as defined in [Table RHBW.6.11](#)), summaries will be provided of the total postbaseline time in the greater-TE-ADA status for patients who were at some point postbaseline in the greater-TE-ADA status group. Postbaseline time in greater-TE-ADA status for each patient will be aggregated.

A by-patient listing to include treatment, visit date, visit, ADA result, TE-ADA result, NAb result, ADA titer value, ixekizumab concentration, ADA and NAb inconclusive results will also be provided for the individual studies, for patients with any 1 sample of ADA (or NAb) positive or inconclusive.

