## 6. Treatment

### 6.1. Treatments Administered

The Blinded Treatment Dosing Period (Period 2) involves a comparison of 2 treatment regimens of ixekizumab, 80 mg Q2W and 80 mg Q4W, to placebo. Each ixekizumab treatment regimen will include patients receiving an 80 mg or a 160 mg starting dose; patients will be randomized to a starting dose at a 1:1 ratio. All doses are administered via SC injection. [Table RHBW.2](#) shows the treatment regimens.

At baseline (Week 0), all patients will receive 2 injections, and will be randomized to a treatment regimen. Patients assigned to an ixekizumab treatment regimen with a 160 mg ixekizumab starting dose will receive 160 mg of ixekizumab as 2 SC injections. Patients assigned to an ixekizumab treatment regimen with an 80 mg starting dose will receive 80 mg of ixekizumab as 1 SC injection, and 1 SC injection of placebo. Patients assigned to the placebo treatment group will receive 2 SC injections of placebo. During the remainder of the Blinded Treatment Dosing Period (Period 2; Week 0 to Week 16), all patients will receive 1 injection every 2 weeks. Details are provided in [Table RHBW.2](#).

During the Extended Treatment Period (Period 3; Week 16 to Week 52), patients originally assigned to either ixekizumab treatment regimen will remain on the same treatment regimen through Period 3. At Week 16, patients originally assigned to placebo will be rerandomized at a 1:1 ratio to ixekizumab 80 mg Q2W or Q4W with a 160 mg starting dose (as two 80 mg SC injections). To maintain the blind, all patients, regardless of treatment group, will receive 2 SC injections at Week 16. Treatment groups in this period are described in [Table RHBW.3](#).

To maintain blinding throughout the study, each patient will receive at least 1 SC injection Q2W regardless of his/her assigned treatment regimen (that is, placebo will be administered every other week as necessary for the Q4W treatment group).

The investigator or his/her designee is responsible for the following:

- explaining the correct use of the investigational product to the patient/patient caregiver
- verifying that instructions are followed properly
- maintaining accurate records of investigational product dispensing, collection, and administration
- returning all unused medication to Lilly or its designee at the end of the study.

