6.1.1. General Considerations for Analyses during the Blinded Treatment Dosing Period (Period 2)

Comparisons between each ixekizumab regimen (80 mg Q2W or 80 mg Q4W) and placebo will be performed for all analyses in Period 2.

Period 2 starts at the first injection of study treatment at Week 0 (Visit 2) and ends before the first injection of study treatment at Week 16 (Visit 8) or the early termination visit (ETV) (between Weeks 0 and 16).

Baseline will be defined as the last available value before the first injection for efficacy, health outcome, and safety analyses. In most cases, this will be the measure recorded at Week 0 (Visit 2). For efficacy measures, if the patient does not take any injection, the last available value on or before randomization date will be used. Change from baseline will be calculated as the visit value of interest minus the baseline value. For safety analyses using a baseline period, the baseline period is defined as the time from Visit 1 to the date/time of the first injection.

The randomization to treatment groups is stratified by country, screening CRP status (nonelevated versus elevated), and number of prior TNF inhibitors used (1 or 2) as described in Section 5.2. The countries will be categorized into geographic regions for analysis. Geographic regions are defined in Section 6.2. Unless otherwise specified, the statistical analysis models will adjust for geographic region, baseline CRP status, and number of prior TNF inhibitors used.

Unless otherwise specified, treatment groups of ixekizumab 80 mg Q2W and Q4W groups will be analyzed without regard to starting dose.

The primary analysis method for treatment comparisons of categorical efficacy and health outcomes variables at specific time points will be made using a logistic regression analysis with treatment, geographic region (Europe and non-Europe), number of prior TNF inhibitors used, and baseline CRP status in the model using PROC Logistic with a Wald test. The odds ratio and 95% CIs will be reported; treatment difference and 95% CI will also be reported. Secondary analysis will be conducted using a Fisher's exact test. In the case when the logistic regression model does not produce statistical results due to sparse data, Fisher's exact test will be used.

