6.1.5. Analysis Populations

The following major analysis populations will be used (additional analysis populations for specific analysis will be defined in the corresponding analysis section):

Intent-to-Treat Population (ITT Population): Unless otherwise specified, efficacy and health outcomes analyses for Period 2 will be conducted on the ITT Population, defined as all randomized patients, even if the patient does not take the assigned treatment, does not receive the correct treatment, or otherwise does not follow the protocol. Patients will be analyzed according to the treatment to which they were assigned.

Per-Protocol Set (PPS): In addition, the primary efficacy analysis will be repeated using the PPS, which is defined as all randomized patients who do not have a subset of important protocol deviations that impact the primary efficacy endpoint (Section 6.14). For example, patients who are not compliant with therapy during the double-blind period will be excluded from the PPS. Compliance with therapy is defined to be missing no more than 20% of expected doses, not missing 2 consecutive doses (all injections in an injection week are counted as 1 dose), and not have any occurrence of over-dosing (that is, took more injections at the same time point than specified in the protocol) during Period 2.

Patients will be analyzed according to the treatment to which they were assigned.

Safety Population: Safety analyses for Period 2 will be conducted on the Safety Population, defined as all randomized patients who received at least 1 dose of study treatment. Patients will be analyzed according to the treatment to which they were assigned in that period.

Extended Treatment Period Population: Efficacy, health outcomes, and safety analyses for Period 3 will be conducted on the Extended Treatment Period Population, defined as all patients who received at least 1 dose of ixekizumab treatment during Period 3.

All Ixekizumab Exposures Safety Population: Safety analyses for combined Blinded Treatment Dosing Period and Extended Treatment Period will be conducted on the All Ixekizumab Exposures Safety Population, defined as all patients who received at least 1 dose of ixekizumab during the study. For each patient, only periods in which ixekizumab is administered are included.

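### SAP 6.12.8.2.1 starts the time-to-antibody clock at the first study injection; if placebo switchers enter the combined-period analysis, that adds about 16 weeks of placebo time to each of them

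*SAP*

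**What the plan says.** SAP 6.12.8.2.1 plans a descriptive time-to-event analysis of TE-ADA (any, low, moderate and high titer) and NAb. The result is in weeks, and the origin in the formula is "Date of first injection of study treatment + 1) / 7". It is stated once, with no period, week or drug attached. Patients without an event are censored at their last immunogenicity assessment. Quartiles with 95% confidence intervals and a Kaplan-Meier plot by treatment group follow if there are enough data.

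On who is included, the section says: "The analyses of ADA effects will be conducted on all evaluable patients within the defined safety population for the Blinded Treatment Dosing Period (Period 2"; the sentence goes on to add Combined Periods 2 and 3. For the combined period it takes its baseline from Table RHBW.6.10 in SAP 6.12.8.1.3. That section says that, for patients not originally randomized to ixekizumab, "baseline is the last nonmissing observation on, or before, the date of the first injection of ixekizumab". The table has a placebo-to-ixekizumab row with baseline Week 16.

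On dosing, Protocol 6.1 says of Week 0: "Patients assigned to the placebo treatment group will receive 2 SC injections of placebo". It then says: "At Week 16, patients originally assigned to placebo will be rerandomized at a 1:1 ratio to ixekizumab 80 mg Q2W or Q4W".

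**The concern.** For a placebo switcher, the event definition and the clock use different starting points. TE-ADA is judged against a Week 16 baseline, so no event can occur earlier. The formula, read literally, starts at the Week 0 placebo injection. The patient then sits in the risk set for 16 weeks in which an event is impossible by definition, and every later event time carries those weeks.

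A reader takes such a plot to show how soon antibodies appear after starting the drug. With switchers pooled in, onset would look later and early cumulative incidence lower than they are. With switchers shown as their own group, their curve would be flat to Week 16 and shifted right.

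**Working it through.** The plan states no figure to reproduce here. The check is date arithmetic, followed by an illustration under stated assumptions.

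**Inputs**
- First study injection: Week 0 in every arm. SAP 6.1.1: "Period 2 starts at the first injection of study treatment at Week 0 (Visit 2". Placebo injections count as study treatment (Protocol 6.1).
- First ixekizumab injection for switchers: Week 16, day 112 ± 4 (Protocol Appendix 2).
- Scheduled antibody samples after the switch: Weeks 24, 28, 36 and 52 (Protocol Appendix 2).
- Planned size: 100 per arm, 300 in total (SAP 5.3).

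**Step 1: the shift.** Let T = (event date − origin + 1)/7. Moving the origin from Week 0 to the first ixekizumab injection changes T by (day of switch)/7:
- 112/7 = 16.0 weeks
- 108/7 = 15.4 weeks and 116/7 = 16.6 weeks at the edges of the window

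**Step 2: a switcher first positive at each scheduled sample.**

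| Sample | Day | As written, (day + 1)/7 | From first ixekizumab, (day − 112 + 1)/7 |
|---|---|---|---|
| Week 24 | 168 | 24.14 | 8.14 |
| Week 28 | 196 | 28.14 | 12.14 |
| Week 36 | 252 | 36.14 | 20.14 |
| Week 52 | 364 | 52.14 | 36.14 |

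**Step 3: the population decides whether the shift occurs.**

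| Combined-period population | Switchers included? | Effect of the formula |
|---|---|---|
| Safety Population initially randomized to ixekizumab (SAP 6.1.3, Table RHBW.6.2, 6.12) | No | None: first study injection and first ixekizumab are both Week 0 |
| All Ixekizumab Exposures Safety Population, "defined as all patients who received at least 1 dose of ixekizumab during the study" (SAP 6.1.5) | Yes | 16 weeks if read literally, against that population's own rule to count only periods on ixekizumab |
| Safety Population, "defined as all randomized patients who received at least 1 dose of study treatment" (SAP 6.1.5, worded for Period 2) | Yes | 16 weeks |

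**Step 4: illustration of the effect on early incidence.** The documents give no TE-ADA rate. Assume switchers are included and pooled, they are one third of exposed patients (100/300, no dropout), the hazard is constant, and a fraction p becomes positive by 16 weeks on drug. By 16 weeks on drug a switcher's last scheduled sample is at 12 weeks on drug (Week 28), so the observed switcher fraction is 1 − (1 − p)^(12/16).
- As written, incidence at 16 weeks = (2/3)p.
- From first ixekizumab, incidence at 16 weeks = (2/3)p + (1/3)[1 − (1 − p)^0.75].

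| Assumed p | As written | From first ixekizumab | Shortfall (points) |
|---|---|---|---|
| 5% | 3.3% | 3.3% + 3.8%/3 = 4.6% | 1.3 |
| 10% | 6.7% | 6.7% + 7.6%/3 = 9.2% | 2.5 |
| 20% | 13.3% | 13.3% + 15.4%/3 = 18.5% | 5.1 |

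A simulation under the same assumptions agrees to within 0.2 percentage points. It also gives a mean time among positives that is 4.3 to 4.5 weeks longer as written (for example 32.1 against 27.8 weeks at p = 5%).

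**Step 5: what does not use this clock.** Overall TE-ADA incidence, titer summaries and NAb proportions are counts. The time-varying status summaries use postbaseline time, which for switchers begins at Week 16. In Period 2 the baseline and the origin are both Week 0.

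**The case against.** The strongest reply is that switchers may not be in this analysis at all. SAP 6.1.3, Table RHBW.6.2 and section 6.12 describe a combined-period safety population limited to patients first randomized to ixekizumab. Where the SAP wants the All Ixekizumab Exposures population it generally names it, and 6.12.8.2.1 does not. The Safety Population definition that includes placebo patients is worded for Period 2. Table RHBW.6.10 is titled for the Extended Treatment Period and may have been borrowed only for its baseline rule. This stands as a real uncertainty: under the restricted population the formula is right. But the section does not say the population is restricted, and the placebo-to-ixekizumab row would then have no use in the combined analysis.

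A second reply is that, if switchers enter through All Ixekizumab Exposures, placebo periods are excluded by that population's definition, and the footnote to Table RHBW.6.10 ties the first study injection to the defined week. A careful programmer might therefore start at Week 16. That is evidence of intent. However, the footnote defines the baseline observation, not the time origin. The population rule conflicts with the formula without rewriting it. SAP 6.1.3 also starts the combined periods at the Week 0 injection, and 6.12.8.1.3 itself distinguishes study treatment from ixekizumab.

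A third reply, that the output is descriptive and conditional on enough data, is correct and limits the importance of the point.

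**Conclusion.** The time origin and the adopted baseline disagree for placebo switchers. The consequence is conditional: if they are included and the formula is applied as written, each switcher's time is overstated by 16.0 weeks (15.4 to 16.6). About 100 patients is a ceiling, reduced by departures before Week 16 and by patients not evaluable for antibodies.

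A reader might infer that the plan definitely biases antibody onset for a third of exposed patients, or that a true 5% will be reported as 3.3%. The documents support neither. Inclusion of switchers is not settled, and the incidences in the illustration are assumed. Even at an assumed 5%, scheduled sampling alone would bring the correctly timed pooled figure to 4.6%, so the part due to the origin is 1.3 points.

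The effect is confined to the combined-period quartiles, their intervals and the Kaplan-Meier plot. No efficacy result, hypothesis test or type I error is touched. This is a minor point worth correcting because the correction is nearly free.

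**What to change.** In SAP 6.12.8.2.1, for Combined Periods 2 and 3, replace the origin with the date of the first ixekizumab injection, at Week 0 or Week 16 according to Table RHBW.6.10. The Period 2 formula can stay.

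In the same place, name the combined-period population: either patients initially randomized to ixekizumab or All Ixekizumab Exposures. If it is the latter, label the time axis of the plot as time since first ixekizumab.

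The cost is two phrases in the SAP and one date variable in the program. Injection dates are already collected, so no new data are needed.
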